8 SELECTION OF STUDY POPULATION

8.1 INCLUSION CRITERIA

Individuals eligible for inclusion in this study must meet all the following criteria:

- 1. Female subjects between the ages of 25-40
- 2. Fitzpatrick skin type I-IV
- 3. Investigator Assessment of Overall Integrated Facial Photodamage of mild to moderate (score of 2 5 inclusive; Section 11.1) and prone to breakouts (non-inflammatory), as assessed by the investigator.
- 4. Willing to withhold use of all other topical skincare products during the study with the exclusion of facial cleansers and Latisse. Make-up is allowed.
- 5. Willing to withhold all facial treatments during the course of the study including toxins, fillers, microdermabrasion, IPL, peels, facials, laser treatments, tightening treatments. Waxing and threading is allowed but not facial laser hair removal.
- 6. Willing to remove all makeup at every visit for pictures.
- 7. Willing to sign Photo release.
- 8. Willing and able to give written informed consent.
- 9. Subject is able to follow study instructions, accessible for treatment and follow-up at the specified time on the specific required study visit days, and likely to complete all study requirements
- 10. Female subjects of child bearing potential agree to take a urine pregnancy test at the Baseline visit, end of the study and when deemed appropriate by Investigator and/or Sponsor. Subjects of childbearing potential is defined as any female who has experienced menarche and who:
 - a. Has not undergone successful surgical sterilization (i.e. hysterectomy or bilateral oophorectomy)

Or

b. Is not post-menopausal (i.e. amenorrhea equal to or greater than 12 consecutive months)

Or

c. Is on hormone replacement treatment (HRT) with a documented serum follicle stimulating hormone (FSH) level of >35mIU/mL

- 11. Be using an acceptable method of contraception throughout the study if they are female of child-bearing potential. Acceptable methods of birth control include: oral and other systemic contraceptives, double barrier, bilateral tubal ligation, partner vasectomy and abstinence. Oral and other systemic contraceptives must be stable for three months prior to the Baseline visit. Patients on oral contraceptives agree not to alter their oral contraceptive, including dose or regimen for the duration of the study

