10 CONCOMITANT MEDICATIONS

Medications in use at study entry should be documented on the CRF. Documentation should include medications that subjects take on an elective or as needed basis. If medications are related to a pre-existing (concomitant) condition or disease this condition or disease will be documented on the Medical History page of the CRF. In general, the addition of a concomitant medication upon or after treatment represents a new adverse event. Worsening of a condition present upon entry or noted as medical history also represents a new AE.

The following medications, preparations, and treatments are prohibited during the study as follows:

- 1. All topical skin care products on the face. Non-medicated facial cleansers are allowed. The use of Latisse is allowed. Makeup is allowed but must be removed for study visits.
- 2. All facial treatments including toxins, fillers, microdermabrasion, IPL, peels, facials, laser treatments, tightening treatments, and facial laser hair removal. Waxing and threading is allowed.
- 3. Oral or topical retinoids.
- 4. Alpha or beta hydroxy acids.

The use of other OTC and prescription medications, exclusive of the medications, preparations, and treatments listed above, are permitted after initiation of the study drug, but must be captured on the appropriate CRF page. If a patient uses any of the above prohibited treatments after initiation of the study drug, contact the medical monitor.

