11 ASSESSMENT OF EFFECTS

11.1 INVESTIGATOR'S SKIN GRADING OF PHOTODAMAGE

At the baseline visit the investigator will assess the facial skin for photodamage based on the grading scale below. The grading scale is a static scale. At each subsequent visit, the investigator will assess the facial skin for effects of treatment with the Obagi 360 system using the same scale. No reference to grading at prior visits will be made. Assessment of the components of photodamage will be made on a 7-point scale as shown below.

Investigator's Skin Grading Scale Manifestations of Facial Photodamage

Overall Rating Scale: 0= None, 1= Minimal, 2-3 = Mild, 4-5= Moderate, 6= Severe

Fine Wrinkling Number and depth of superficial wrinkles, fine lines typically

appearing in periorbital and perioral regions,

Mottled Assessment of light patchy mottled hyperpigmentation and solar

Hyperpigmentation freckling based on qualitative criteria such as area/density of

pigment, color intensity, uniformity of distribution

Sallowness Visual assessment of color tone from pink or rosy to very sallow or

pale- The opposite of radiance

Loss of texture Visual assessment of surface properties of the skin, i.e., skin grain

and smoothness

Pore visibility Appearance of pores, especially on the nose and cheek areas

Breakouts Small non-inflammatory acneic lesions

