12 SAFETY EVALUATIONS

12.1 SAFETY ASSESSMENTS – ADVERSE EVENTS (AE)

An AE is any untoward medical occurrence in a subject or clinical investigation subject administered a study product and which does not necessarily have a causal relationship with the study product. An AE can therefore be any unfavorable and unintended sign (including a clinically significant abnormal laboratory finding), symptom, or disease temporally associated with the use of an investigational or marketed study product, whether or not considered related to the investigational or marketed study product.

AEs include any illness, sign, symptom, or out-of-range AND clinically significant laboratory finding that has appeared or worsened during the course of the clinical study, regardless of causal relationship to the study product(s). The collection of non-serious AE information should begin at initiation of study product. Serious AEs (SAEs) should be collected from the time that the subject provides informed consent, which is obtained prior to the subject's participation in the clinical study, i.e., prior to undergoing any study-related procedure and/or receiving investigational product, through and including 30 calendar days after the last administration of the investigational product. Any SAE occurring after study completion must be promptly reported if a causal relationship to investigational product is suspected.

An evaluation of adverse experiences will be performed at each visit. The subject will be questioned to determine if any adverse events have been experienced since the last visit. All adverse events, regardless of perceived relationship to investigational product, will be reported and recorded on the appropriate case report forms. Any significant new abnormality will be recorded and followed until the abnormal finding returns to normal for that subject.

When a concomitant medication/therapy is reported during the study that is not related to medical history, a corresponding Adverse Event form will be completed and the reason for the treatment documented.

When a drug-related adverse event persists at the end of the study, the investigator will conduct follow-up contacts with the subject until the investigator/sponsor agree the event is satisfactorily resolved and/or stabilized.

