12.1.2 RELATEDNESS OF ADVERSE EVENT

The relationship of an adverse event to investigational product is to be assessed by the investigator according to the following definitions:

Related:

There is a relationship between the event and treatment with the investigational product or there is a reasonable possibility that there is evidence to suggest a causal relationship, follows a temporal relationship of the event to study drug administration and cannot be reasonably explained by other factors (such as the subject's clinical state, concomitant therapy and/or other interventions). The following types of evidence would suggest a causal relationship between investigational product and AE: a single occurrence of an event that is uncommon and known to be strongly associated with drug exposure (angioedema, hepatic injury, Stevens-Johnson Syndrome), one or more occurrences of an event that is not commonly associated with drug exposure, but is otherwise uncommon in the population exposed to the drug (tendon rupture), an aggregate analysis of specific events observed in a clinical trial that indicated those events occur more frequently in the drug treatment group than in a concurrent or historical group.

Not Related: There is not a possibility that the AE is related to the investigational product. There is Data is available to clearly identify an alternative cause for the event (e.g., antigen in a case of suspected drug-induced hepatitis, hemorrhage due to mechanical injury)

Note: An alternative etiology must be provided by the investigator if the event is deemed Not Related

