12.2 TOLERABILITY EVALUATIONS

The investigator will assess the tolerability of the Obagi 360 system at each visit. Tolerability will be graded on a 4-point scale (0 - none to 3 - severe) for each of the following:

- Dryness/Scaling
- Erythema
- Burning/Stinging
- Itching

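### Facial waxing and threading are permitted with no interval before visits and no explicit requirement to record them, so transient hair-removal reactions can enter the tolerability proportions and cannot be separated out afterwards

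*Protocol*

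**What the plan says.** The permission appears in the Synopsis, in Section 8.1 and in Section 10. Inclusion criterion 5 lists facial treatments to be withheld and then adds: "Waxing and threading is allowed but not facial laser hair removal". Section 10, item 2, repeats the ban and the exception: "Waxing and threading is allowed". No interval before a visit is attached in any of the three places.

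Section 10, item 1, does attach a visit-day condition to another permitted item: "Makeup is allowed but must be removed for study visits".

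On recording, Section 10 says that other OTC and prescription medications "are permitted after initiation of the study drug, but must be captured on the appropriate CRF page". Hair removal is not named there, nor in Table 1 or the visit lists of Sections 13.1 and 13.2. Section 12.1 adds a more general rule: "When a concomitant medication/therapy is reported during the study that is not related to medical history, a corresponding Adverse Event form will be completed".

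On tolerability, Section 12.2 says: "The investigator will assess the tolerability of the Obagi 360 system at each visit". Four signs (dryness/scaling, erythema, burning/stinging, itching) are each graded 0 to 3. Table 1 and Sections 13.1 and 13.2 schedule this at Visits 2 to 5 only. Section 14.2.5.2 summarizes the proportion of subjects in each grade by visit.

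**The concern.** Waxing and threading act on the same facial skin that is graded for redness, scaling, stinging and itching. If a subject has had hair removal shortly before a visit, a short-lived local reaction may be present when the grades are taken. The tolerability scale has no place for a cause, and every grade counts towards the proportions reported for the system.

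A controlled trial would carry the same background in both arms, and the comparison would allow for it. This study is single-arm, so the proportions are read directly as the product's tolerability. An SAP could flag or set aside affected grades only if the date of hair removal had been collected, so the gap has to be closed in the protocol and the CRF.

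**Working it through.** **Can the effect enter the table, and can it be taken out again?**

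1. Timing: Section 10 conditions makeup on the study visit and sets no such condition for waxing or threading.
2. Record: the CRF capture rule in Section 10 concerns medications. The compliance review (Section 9.6) mentions refraining from prohibited treatments, and hair removal is permitted. No section explicitly requires its date or site.
3. Attribution: Section 12.1.2 has the investigator weigh other interventions when judging the cause of an adverse event. Section 12.2 has no matching step for tolerability grades.
4. Reference: there is no comparator (Synopsis; Section 7.2) and no scheduled baseline tolerability grade (Table 1; Section 13.1).

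A reaction can therefore enter the proportions, and the data that the protocol requires do not identify it.

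**How large could it be?** The protocol gives no figure to reproduce. From the documents: 40 subjects (Section 14.3) and follow-up visits on Days 14, 28, 56 and 84 (Section 13.2). Assumed: a share s = 0.5 of subjects has facial hair removal once every 28 days, and the effect is visible for d = 1 to 3 days.

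- Weight of one subject: 1/40 = 2.5 percentage points in a tolerability category at that visit.
- Any single visit: s × d/28. For d = 1, 0.5 × 1/28 = 1.8%. For d = 3, 0.5 × 3/28 = 5.4%. Of 40 subjects this is 0.7 to 2.1.
- One or more of the four follow-up visits, regular 28-day cycle and visits exactly on schedule: Days 28, 56 and 84 fall at the same point of the cycle and only Day 14 differs, so the formula is s × 2d/28. For d = 1, 0.5 × 2/28 = 3.6%. For d = 3, 0.5 × 6/28 = 10.7%.
- One or more of the four, visits treated as independent: s × [1 − (1 − d/28)^4]. For d = 1, 0.5 × [1 − (27/28)^4] = 0.5 × 0.135 = 6.8%. For d = 3, 0.5 × [1 − (25/28)^4] = 0.5 × 0.364 = 18.2%.

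Visit windows and irregular grooming would put the any-visit figure between the last two lines.

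**Sensitivity to the share of users, at any single visit:**

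| Share with hair removal (assumed) | d = 1 | d = 3 |
|---|---|---|
| 0.25 | 0.9% | 2.7% |
| 0.50 | 1.8% | 5.4% |
| 1.00 | 3.6% | 10.7% |

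Hair removal timed just before photograph days would raise these figures. Avoiding it before visits would lower them.

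**The case against.** The strongest reply is that this is a considered choice. The sponsor thought about hair removal, banned the laser form, allowed waxing and threading, and said so consistently in three places. Nothing is contradictory, the tolerability table is descriptive, and about 1 to 2 subjects of 40 per visit is little. That stands, and it is why the point is minor.

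A second reply is that partial safeguards exist. Subjects are questioned about adverse events at each visit, a reported concomitant therapy triggers an Adverse Event form, and causality weighs other interventions. An investigator examining the face may also recognise a local reaction and not score it against the product. This stands in part. The protocol does not say that routine hair removal counts as a therapy, and the causality step belongs to adverse events. It gives the investigator no instruction to leave such redness out of the tolerability grade.

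Three stronger readings are tempting, and the documents do not support them:

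- A reader might infer that hair removal is expressly allowed on the day of a visit. The protocol is silent on timing and does not say this.
- A reader might infer that hair removal goes unrecorded. The CRF is not among the documents, so only the lack of an explicit requirement can be stated.
- A reader might extend the point to the efficacy grades, since loss of texture is a "Visual assessment of surface properties of the skin". The documents do not show that hair removal changes skin grain or smoothness, or in which direction. On a regular 28-day cycle, Baseline would share its phase with Days 28, 56 and 84, so any such effect would tend to cancel in the paired change.

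**Conclusion.** The point holds as a small, cheap improvement to the tolerability data. A permitted facial procedure has no timing rule and no explicit recording requirement, while the grades it could affect are unattributed, uncontrolled and reported as tolerability of the system. That reactions *can* enter the proportions follows from the text. That they *will*, and how often, does not.

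The size rests wholly on assumptions: half the subjects, a 28-day cycle, 1 to 3 days of visible effect, and a reaction that the investigator would score. On these, about 1.8-5.4% of subjects are affected at any visit, and between 3.6-10.7% and 6.8-18.2% at one or more follow-up visits, depending on whether visits share a phase of the grooming cycle. No conclusion about the photodamage scores follows.

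**What to change.** In criterion 5 (Section 8.1 and the Synopsis) and Section 10, item 2, state one fixed interval without facial waxing or threading before Baseline and before each of Visits 2 to 5. The sponsor and investigator should choose its length. At each visit, record the date and facial site of the last hair removal. Tolerability grades taken within the interval can then be flagged, and the proportions shown with and without them in a sensitivity summary.

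The cost is one line of subject instruction, one CRF entry per visit and slight inconvenience to subjects.

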11 ASSESSMENT OF EFFECTS

11.1 INVESTIGATOR'S SKIN GRADING OF PHOTODAMAGE

At the baseline visit the investigator will assess the facial skin for photodamage based on the grading scale below. The grading scale is a static scale. At each subsequent visit, the investigator will assess the facial skin for effects of treatment with the Obagi 360 system using the same scale. No reference to grading at prior visits will be made. Assessment of the components of photodamage will be made on a 7-point scale as shown below.

Investigator's Skin Grading Scale Manifestations of Facial Photodamage

Overall Rating Scale: 0= None, 1= Minimal, 2-3 = Mild, 4-5= Moderate, 6= Severe

Fine Wrinkling Number and depth of superficial wrinkles, fine lines typically

appearing in periorbital and perioral regions,

Mottled Assessment of light patchy mottled hyperpigmentation and solar

Hyperpigmentation freckling based on qualitative criteria such as area/density of

pigment, color intensity, uniformity of distribution

Sallowness Visual assessment of color tone from pink or rosy to very sallow or

pale- The opposite of radiance

Loss of texture Visual assessment of surface properties of the skin, i.e., skin grain

and smoothness

Pore visibility Appearance of pores, especially on the nose and cheek areas

Breakouts Small non-inflammatory acneic lesions

11.1.1 INVESTIGATOR FACIAL PHOTODAMAGE CHARACTERISTICS ASSESSMENT

Efficacy evaluations for each of the following dermatological characteristics will be conducted according to Table 2: fine wrinkling, mottled hyperpigmentation, sallowness, loss of texture, pore visibility, and breakouts.

Table 2 Investigator's Skin Grading Scale

Invest	Investigator Assessment of Manifestations of Facial Photodamage								
	FAC	IAL PHOTO	DAMAGE S	SKIN GRA	ADING SC	ORE			
Severity	FINE WRINKLING (circle one)	MOTTLED HYPER- PIGMENTATION (circle one)	SALLOWNESS (circle one)	LOSS OF TEXTURE (circle one)	PORE VISIBILITY (circle one)	BREAKOUTS (circle one)			
None	0	0	0	0	0	0			
Minimal	1	1	1	1	1	1			
Mild	2	2	2	2	2	2			
Mild	3	3	3	3	3	3			
Moderate	4	4	4	4	4	4			
Moderate	5	5	5	5	5	5			
Severe	6	6	6	6	6	6			

11.1.2 INVESTIGATOR ASSESSMENT OF OVERALL INTEGRATED FACIAL PHOTODAMAGE

Efficacy evaluation for overall integrated facial photodamage will also be conducted according to Table 3.

Table 3 Investigator Assessment of Overall Integrated Facial Photodamage

Score	Overall Facial Photodamage				
0	None				
1	Minimal				
2) (1)				
3	Mild				
4	Madausta				
5	Moderate				
6	Severe				

CONFIDENTIAL AND PROPRIETARY INFORMATION OF OMP, INC.

11.2 PHOTOGRAPHS

The following instructions will be used to obtain photographs at each visit. Detailed instructions are provided in the Photography Manual.

- 1. Instruct subject to remove all makeup including eye makeup and lipstick.
- 2. Wipe subject's face with make-up remover to remove any residual makeup and apply blotting papers to eliminate shine (both items will be provided by sponsor).
- 3. Clear all hair away from face with headband (provided by sponsor).
- 4. Place white drape over subject's clothes (provided by sponsor).
- 5. Using the Visia camera system (Canfield Scientific), be sure the stool height is adjusted, the subject is sitting up straight and the subject has a neutral, relaxed facial expression with eyes open. Each subject will have a frontal, right oblique, and left oblique picture taken with specified filters: Standards, parallel polarized, perpendicular polarized, UV, fluo and UV spots.
 - For frontal view: subject's chin should be centered and gently resting in the chin cup. The subject's head, neck and spine should be aligned and she should face the booth squarely in the appropriate direction for the view.
 - For right oblique view: position the forehead support and the chin cup on the right side of the device. Have subject rest chin in cup and tilt forward until positioned.
 - For left oblique view: position the forehead support and the chin cup on the left side of the device. Have subject rest chin in cup and tilt forward until positioned.

All images will be captured on a flash drive and sent to the sponsor at the end of the first month of the study, the middle of 2 month of the study and at the end of the study.

11.3 SUBJECT'S SELF-ASSESSMENT

At each visit after baseline the subject will complete a self-assessment using the scales provided in Appendix 2 and/or Appendix 3, based on visit requirements.

12 SAFETY EVALUATIONS

12.1 SAFETY ASSESSMENTS – ADVERSE EVENTS (AE)

An AE is any untoward medical occurrence in a subject or clinical investigation subject administered a study product and which does not necessarily have a causal relationship with the study product. An AE can therefore be any unfavorable and unintended sign (including a clinically significant abnormal laboratory finding), symptom, or disease temporally associated with the use of an investigational or marketed study product, whether or not considered related to the investigational or marketed study product.

AEs include any illness, sign, symptom, or out-of-range AND clinically significant laboratory finding that has appeared or worsened during the course of the clinical study, regardless of causal relationship to the study product(s). The collection of non-serious AE information should begin at initiation of study product. Serious AEs (SAEs) should be collected from the time that the subject provides informed consent, which is obtained prior to the subject's participation in the clinical study, i.e., prior to undergoing any study-related procedure and/or receiving investigational product, through and including 30 calendar days after the last administration of the investigational product. Any SAE occurring after study completion must be promptly reported if a causal relationship to investigational product is suspected.

An evaluation of adverse experiences will be performed at each visit. The subject will be questioned to determine if any adverse events have been experienced since the last visit. All adverse events, regardless of perceived relationship to investigational product, will be reported and recorded on the appropriate case report forms. Any significant new abnormality will be recorded and followed until the abnormal finding returns to normal for that subject.

When a concomitant medication/therapy is reported during the study that is not related to medical history, a corresponding Adverse Event form will be completed and the reason for the treatment documented.

When a drug-related adverse event persists at the end of the study, the investigator will conduct follow-up contacts with the subject until the investigator/sponsor agree the event is satisfactorily resolved and/or stabilized.

AEs should be followed to resolution or stabilization, and reported as SAEs if they meet the criteria for SAE. The investigator will instruct the subject to report any adverse events that may occur during the study. At each visit, the investigator should ask the subject, in a non-directive fashion, about any change in the subject's overall condition since the previous visit. All AEs will be recorded in the CRF.

Each AE, which appears to be independent of any prior event, will be reported separately. The description will include the nature of the adverse event, the date of onset, the severity (Section

CONFIDENTIAL AND PROPRIETARY INFORMATION OF OMP, INC.

14.1.1) of each event, the investigator's opinion regarding the likelihood of causal relationship (Section 14.1.2) to study drug, the course of action taken, the date of resolution, and the outcome of the event.

